#### 6.2.4 Dose Limiting Toxicities

DLTs will be used to determine dose escalation, dose de-escalation, and the MTD (if reached), using the National Cancer Institute (NCI)-Common Terminology Criteria for Adverse Events Version 4.03 (CTCAE 4.03).

DLTs are defined as any Grade  $\geq 3$  AEs and irAEs, during treatment of either M4112 as single agent **CCI** by the Investigator and/or the Sponsor, during Cycle 1 at any dose level:

- Any Grade  $\geq 3$  nonhematological AE or irAE assessed by the Investigator or Sponsor during the first Cycle (first 28 days) of study treatment **except**:
  - Diarrhea of  $\leq 6$  days duration following adequate and optimal therapy that resolves to Grade  $\leq 1$
  - Grade 3 skin toxicity that resolves to Grade 1 or less with supportive measures within 7 days
  - Nausea and vomiting of  $\leq 72$  h duration with adequate and optimal therapy
  - Single laboratory values out of the normal range that have no clinical correlate, and resolve to Grade  $\leq 2$  within 6 days with adequate medical management (except Grade  $\geq 3$  liver function test increase without any clinical correlate)

- e. Grade 3 infusion-related reactions resolving within 6 h from the end of infusion and controlled with medical management
- f. Transient ( $\leq 72$  h) Grade 3 fatigue, local reactions, flu-like symptoms, fever, headache that resolves to Grade  $\leq 1$  with adequate treatment
- g. Keratoacanthoma and SCC of the skin. Any suspicious skin lesion that is local and should be resected with negative resection margin
- h. Symptomatic thyroid dysfunction which is manageable with adequate treatment and resolves to Grade 2 within 6 days
- i. Tumor flare phenomenon defined as local pain, irritation, or rash localized at sites of known or suspected tumor that resolve to Grade 2 within 6 days
- j. Asymptomatic Grade  $\geq 3$  lipase or amylase elevation not associated with clinical manifestations of pancreatitis.
- Any TEAE observed in subsequent cycle that in the opinion of the SMC needs to be taken into account for the overall evaluation of the safety and proposal of dose escalation
- Any Grade 4 neutropenia of  $> 5$  days duration, Grade  $\geq 3$  febrile neutropenia
- Grade 3 hemoglobin decrease ( $< 8.0$  g/dL) despite blood transfusion or erythroid growth factor
- Grade 4 hemoglobin decrease assessed as related to study drug
- Any Grade 4 thrombocytopenia or Grade 3 thrombocytopenia with bleeding

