- Immunotherapy including interferon, immunosuppressive drugs (eg, chemotherapy or systemic corticosteroids except for short term treatment of allergic reactions, endocrine replacement therapy at low dose prednisone [ $\leq 10$  mg daily] or equivalent, or for the treatment of irAEs or other appropriate short term steroid use), or other experimental pharmaceutical products. Short term administration of systemic steroid or other immunosuppressant such as infliximab or mycophenolate (ie, for allergic reactions or the management of irAEs) is allowed. Steroids with no or minimal systemic effect (topical, inhalation) are allowed.  
Note: for subjects with glioblastoma, steroid use is allowed

- Adefovir
- Prophylactic use of corticosteroids for infusion related reactions is prohibited
- Any live vaccine therapies for the prevention of infectious disease within 28 days prior to study entry and during study. Administration of inactivated vaccines is allowed (eg, inactivated influenza vaccines)
- Blood transfusions and erythroid growth factors are not allowed during the 28-day DLT window during the escalation phase. These subjects are considered to have had a DLT if the drop in hemoglobin is rated as drug related, or subjects are regarded as not evaluable, if the event is not related to study medication.

If the administration of a nonpermitted concomitant drug becomes necessary during the study, the subject will be withdrawn from study treatment (the Medical Monitor should be contacted to discuss whether the IMP must be discontinued).

[figure not shown]

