## 8.4 Analysis Sets

For purposes of analysis, the following populations are defined in Table 13. CCI

Table 13 Analysis Sets

Population	Description
Screening	All participants who sign informed consent.
Dose Escalation	All subjects treated in dose escalation cohorts who do not miss > 5 planned total daily doses of M4112 CCI in the first cycle (first 28 days) of the dose escalation part for other than DLT. The CCI
Safety	The Safety Analysis Set will include all subjects who receive at least 1 dose of study treatment. CCI
Concentration-QTc Analysis Set	The cQTc Analysis Set will include all subjects with at least baseline and one on treatment measurement of time-matched ECG and M4112 plasma concentration collected during the dose-escalation phase. The cQTc analysis set will be used for slope analysis of exposure response in QTc analysis.
M4112 Pharmacokinetic	All subjects from the Safety Analysis Set without major protocol deviations/violations or events that would affect PK. Subjects in the PK Analysis Set must have received at least 1 dose of M4112 and must have sufficient M4112 plasma concentration data to enable the calculation of at least 1 PK parameter. Sufficient concentration data is defined as at least 3 valid, postdose concentration points in the PK profile to obtain any PK parameter.
Pharmacodynamics	All subjects who received at least 1 dose of M4112 and provide the predose and at least 1 postdose sample for PD assessment.

ADA = anti-drug antibody; cQTc = concentration-corrected QT interval (QTc); DLT = dose-limiting toxicities; ECG = electrocardiogram; PD = pharmacodynamics; PK = pharmacokinetic.

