## 8.2 Definition of Analysis Sets and Subgroups

The analysis sets of subjects whose data will be included in the analyses described in this IAP are defined in [Table 1](#).

**Table 1** Analysis Sets

Population	Description
Screening (SCR)	All subjects who sign informed consent.
DLT	All subjects who received at least one dose of study intervention and meet at least one of the following criteria: 

- Received at least 5 planned cumulative total daily doses of M4112 in the first cycle (first 28 days) or

- Experienced at least one DLT during the DLT period, regardless of the administered number of doses of study intervention/completion of the DLT period

Safety	The Safety Analysis Set will include all subjects who receive at least 1 dose of study treatment.
Concentration-QTc Analysis Set	The cQTc Analysis Set will include all subjects with at least baseline and one on treatment measurement of time-matched ECG and M4112 plasma concentration collected during the dose-escalation phase.
M4112 Pharmacokinetic	All subjects from the Safety Analysis Set without clinically important protocol deviations/violations or events that would affect PK (see Section 8.1 ). Subjects in the PK Analysis Set must have received at least 1 dose of M4112 and must have sufficient M4112 plasma concentration data to enable the calculation of at least 1 PK parameter. Sufficient concentration data is defined as at least 3 valid, postdose concentration points in the PK profile to obtain any PK parameter.
Pharmacodynamics	All subjects who received at least 1 dose of M4112 and provide the predose and at least 1 postdose sample for Pd assessment.

cQTc = concentration-QTc response; DLT = dose-limiting toxicities; ECG = electrocardiogram;

Pd = pharmacodynamics; PK = pharmacokinetic; QTc = corrected QT interval.

There are no subgroup analyses planned for this study.

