### 15.1 Dose Limiting Toxicities

The occurrence of dose limiting toxicities (DLTs) during the DLT evaluation period (i.e., during the first treatment cycle of 28 days) is a primary endpoint of this study. The DLT set will be used for the analysis of the primary endpoint. Please refer to [Section 6.2.4](#) of the Clinical Study Protocol MS201408-0005 for the detailed definition of a DLT.

The number and proportion of subjects experiencing DLTs will be reported by dose level. Posterior probabilities (2.5%, 25%, 50%, 75%, and 97.5% quantiles) for a DLT by tested dose level will be estimated using the BLRM specified in the protocol.

Details of the DLTs will be presented in a listing sorted by SOC and PT, including: DLT, SOC, PT, relationship to M4112, seriousness, dose group, time since last and first administration of M4112, and subject's age/sex/site of primary tumor.

In addition, a DLT profile plot of all subjects in the Safety Analysis Set will be produced. This will show a closed square for all subjects who were considered evaluable (in DLT set) and did not have a DLT during Cycle 1, an open square for those who experienced a DLT during Cycle 1, and an open circle for those who were excluded from the DLT Set. This plot will have Cohort Number on the x-axis and dose level (mg) on the y-axis.

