**10 Analysis Sets**

Analysis sets relevant to SMCs are defined in Table 1.

**Table 1** Analysis Sets

Population	Description
Screening	All participants who sign informed consent.
Dose Escalation	All subjects treated in dose escalation cohorts who do not miss > 5 planned total daily doses of M4112 CCI in the first cycle (first 28 days) of the dose escalation part for other than DLT. The latter only applies to subjects in the combination dose escalation.
Safety	The Safety Analysis Set will include all subjects who receive at least 1 dose of study treatment. In case of combination treatment, study treatment includes also the combination agents.
M4112 Pharmacokinetic	All subjects from the Safety Analysis Set without major protocol deviations/violations or events that would affect PK. Subjects in the PK Analysis Set must have received at least 1 dose of M4112 and must have sufficient M4112 plasma concentration data to enable the calculation of at least 1 PK parameter. Sufficient concentration data is defined as at least 3 valid, postdose concentration points in the PK profile to obtain any PK parameter.
Pharmacodynamics	All subjects who received at least 1 dose of M4112 and provide the predose and at least 1 postdose sample for PD assessment.

ADA = anti-drug antibody; cQTc = concentration-corrected QT interval (QTc); DLT = dose-limiting toxicities; ECG = electrocardiogram; PD = pharmacodynamics; PK = pharmacokinetic.

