#### Bayesian two-parameter logistic model

Upon completion of the DLT observation period of each cohort, summary statistics of the posterior probability distribution of the true DLT rate (2.5%, 25%, 50%, 75%, and 97.5% quantiles) for each predefined dose level will be updated and estimated according to the logistic model. Using data from all subjects completing the DLT period or experiencing a DLT during this period at the completion of a new cohort (and data from all previous cohorts: DE analysis set), the Bayesian logistic model provides a recommended dose level for the next cohort.

Recommendation is based on a loss function (probabilities of being in 1 of the 4 intervals will be multiplied with a loss term as follows:

$0 * P(\text{target dosing (estimated DLT rate in (0.17-0.35])}) + 1 * P(\text{for over dosing (estimated DLT rate in (0.35-0.67]) or under dosing (estimated DLT rate in [0-0.17])}) + 2 * P(\text{excessive dosing (estimated DLT rate in (0.67-1])})$ .

In addition, only doses with estimated probability of  $\leq 25\%$  that the true DLT rate is more than 35% (overdose control) will be recommended by the model. The recommended dose level resulting from the model for the next cohort is the dose with the lowest loss function from all doses fulfilling the overdose control rule. This Bayesian escalation approach will be used to assist the SMC to select the next dose from a predicted set of acceptable doses, i.e., 100 mg, 200 mg, 400 mg, 600 mg, 800 mg and 900 mg BID. It is possible to choose a dose(s) not within the pre-specified dose-escalation plan. Using a Bayesian model-based design aids the SMC in dosing decisions by providing more information compared to a 3+3 design (e.g., an estimated dose-toxicity curve with confidence information utilizing data on all subjects in DE analysis set at time of analysis).

The model will continue to be updated at each SMC until the SMC has decided to stop dose escalation.

Prior distribution and likelihood are used to calculate the posterior probabilities based on Bayes theorem.

The likelihood is defined based on a binomial distribution, modelling the rate of subjects with at least 1 DLT.

The prior distribution is set-up as follows:

The relationship between dose and toxicity rate is defined by

$$P(DLT|d_j, \alpha, \beta) = \frac{\exp\left(\alpha + \exp(\beta) * \log\left(\frac{d_j}{d_{ref}}\right)\right)}{1 + \exp\left(\alpha + \exp(\beta) * \log\left(\frac{d_j}{d_{ref}}\right)\right)}$$

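### The final IAP's DLT set keeps, as evaluable and DLT-free, a subject whom Protocol 6.5.2 calls not evaluable after an in-window transfusion for an unrelated hemoglobin drop

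*Protocol*

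**What the plan says.** Protocol 6.5.2 prohibits blood transfusion and erythroid growth factors during the DLT window of the escalation phase. Subjects who receive them are "considered to have had a DLT if the drop in hemoglobin is rated as drug related, or subjects are regarded as not evaluable", the latter when the event is not related to study medication.

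The final IAP does not carry this rule over:

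- **IAP 8.2, Table 1 (DLT set).** A treated subject enters by having a DLT, or by the dosing criterion "Received at least 5 planned cumulative total daily doses of M4112 in the first cycle". Transfusion is not mentioned.
- **IAP 15.1 (plot).** The DLT profile plot gives a closed square to subjects "considered evaluable (in DLT set) and did not have a DLT during Cycle 1". Being in the set and being evaluable are therefore the same thing.
- **IAP 15.1 (definition).** The reader is sent to Section 6.2.4 "of the Clinical Study Protocol MS201408-0005 for the detailed definition of a DLT". Section 6.5.2 is not cited.

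Protocol 6.2.4 lists Grade 3 hemoglobin below 8.0 g/dL "despite blood transfusion or erythroid growth factor" as a DLT and does not repeat the 6.5.2 rule.

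The Dose Escalation sets used during the trial also lack the class. Protocol 8.4, Table 13, and the SMC iAP (appended to the final IAP), Section 10, Table 1, exclude only for more than 5 missed total daily doses "in the first cycle (first 28 days) of the dose escalation part for other than DLT".

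**The concern.** The occurrence of DLTs is a primary endpoint, and the protocol says who counts in its denominator. A programmer who follows IAP Table 1 and Section 15.1 literally would count a subject whom the protocol calls not evaluable, and would count that subject as a non-DLT. The error has one direction: keeping a non-DLT subject can only lower the estimated DLT rate. Dose levels hold 3 to 6 subjects, so one subject is a visible share of the denominator. At stake are the reported DLT proportion by dose level and the posterior quantiles in IAP 15.1.

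**Working it through.** **Step 1: place one case in each set.** Take a subject with an unrelated hemoglobin drop, transfused in Cycle 1, with no other DLT.

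- *Protocol 6.5.2:* not evaluable.
- *Final IAP DLT set:* included once the dosing criterion is met, then shown as evaluable without a DLT.
- *Protocol and SMC Dose Escalation sets:* 6.5.2 also calls for withdrawal after a nonpermitted treatment. With full dosing until then, missed daily doses = 28 − last dosing day. A last dose on Day 22 gives 28 − 22 = 6 > 5, so the subject is excluded. A last dose on Day 23 gives 28 − 23 = 5, so the subject is not excluded. What remains is a very late transfusion, or dosing that continues after discussion with the Medical Monitor.

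**Step 2: check the model.** Inputs from Protocol 8.5.2 and SMC iAP 16.1: logit p(d) = α + exp(β)·log(d/900), with α ~ N(−0.8001, 1.5²), β ~ N(0.4647, 1.5²) and covariance 0. The loss is 0 for (0.17, 0.35], 1 for under- or overdosing and 2 for above 0.67. A dose is admissible if P(p > 0.35) < 25%. The posterior is proportional to prior × ∏ p^x (1 − p)^(n − x), integrated on a grid. This reproduces all 18 recommended doses in Protocol Appendix V. Scenario 4b, for example, gives 800 mg with interval probabilities 0.418/0.358/0.204/0.021, against 0.42/0.36/0.21/0.02 in the appendix.

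**Step 3: effect on the final report.** Protocol 8.1 anticipates 4 levels of 3 subjects, 2 levels of 6, and 2 DLTs. It does not say where the DLTs fall. I assume 6 subjects each at 800 and 900 mg, no DLT at lower doses, and one unrelated case at 900 mg. Posterior figures are for 900 mg.

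| DLT placement | Quantity at 900 mg | Case kept | Case removed |
|---|---|---|---|
| 1 at 800 mg, 1 at 900 mg | Observed rate | 1/6 = 16.7% | 1/5 = 20.0% |
| | Posterior median | about 17.5% | about 19.1% |
| | 97.5% quantile | about 45.8% | about 49.9% |
| | Recommended dose | 900 mg | 900 mg |
| Both at 900 mg | Observed rate | 2/6 = 33.3% | 2/5 = 40.0% |
| | Posterior median | about 21.5% | about 24.3% |
| | 97.5% quantile | about 56% | about 62% |
| | Recommended dose | 900 mg | 800 mg |

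IAP 15.1 reports the proportions and quantiles. The recommended dose is shown only as a measure of sensitivity.

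**Step 4: range over other data.** I set earlier cohorts at 0/3 and varied the last cohort over the six doses.

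- *No DLT* (0/3 vs 0/2, 0/6 vs 0/5): the recommendation changes in 0 of 12 settings.
- *With a DLT* (1/3 vs 1/2, 1/6 vs 1/5, 2/6 vs 2/5): it changes in 6 of 18. Every change is to a less conservative recommendation when the case is kept. At 600 mg, 1/6 vs 1/5 gives 800 vs 600 mg, with P(p > 0.35) at 800 mg of 0.225 vs 0.256.
- Over those 18 settings the posterior median at that dose is 1.0 to 6.3 percentage points lower, and the 97.5% quantile 3.1 to 11.3 points lower, when the case is kept.
- On Appendix V's own scenarios, 4 of 18 recommendations change (1a, 4b, 5b, 6a), each with one DLT already observed.

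**The case against.** **The protocol already limits the model to evaluable subjects.** Section 8.5.2 says the Bayesian model is updated with data from evaluable subjects, and 6.5.2 says who is not evaluable. The SMC iAP (16.1) adds a completer rule, "Using data from all subjects completing the DLT period or experiencing a DLT during this period", which a subject withdrawn before Day 28 arguably does not meet. The SMC also receives patient profiles with concomitant medications and procedures, and may depart from the model. This stands for the escalation phase and reduces the gap there to the residue in Step 1. It does not help the final report, where IAP Table 1 defines the set and 15.1 calls its members evaluable.

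**Deviation review could remove the subject.** IAP 18.1 lists only deviations found by programming. Medical review can identify others, and IAP 10.2.2 tabulates exclusions for each population. So the absence of transfusion from 18.1 proves little. But only the PK set's definition refers to deviations. The DLT set's definition gives no ground for removing a subject who meets it.

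**A reader might infer that 6.2.4 contradicts 6.5.2,** because the Grade 3 criterion presupposes a barred treatment. The documents do not support that. Section 6.2.4 is a list in which any one item suffices, 6.5.2 adds a further route to a DLT, and a prohibited transfusion can still be given. A related, transfused drop is a DLT under 6.5.2 and must be recorded as one in the eCRF (7.4.1.4). It is missed only if 6.2.4 is read alone and no other DLT criterion is met, which is why the single citation in IAP 15.1 should be widened.

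**The effect needs a chain of events:** an unrelated transfusion, a subject not otherwise excluded, and a DLT in another subject. That is fair. Protocol 8.1 expects few DLTs, and two of the six changes in Step 4 only just cross the 25% limit.

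**Conclusion.** The point holds for the final IAP. Followed literally, it puts a subject whom the protocol calls not evaluable into the denominator of a primary endpoint, as a non-DLT. In the planned-size scenario this lowers the observed rate at 900 mg by 3.3 points (16.7% vs 20.0%) or 6.7 points (33.3% vs 40.0%), depending on where the assumed DLTs fall. The posterior median falls by roughly 1.6 or 2.8 points.

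The figures assume one such case, with no other DLT of its own, at a dose where another subject had a DLT. The documents give no transfusion rate, so the likelihood cannot be stated.

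Two stronger conclusions are tempting and unsupported. One is that escalation decisions were distorted: the protocol and SMC rules largely prevent that, and IAP Sections 6 and 7 show that Part IA is complete with one abbreviated final analysis left. The other is to blame this omission for the full breadth of the IAP set, most of which comes from its separate minimum-dose criterion.

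It should be corrected, but the consequence is confined to reported DLT rates and posterior quantiles.

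**What to change.** Before database lock:

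1. In IAP 8.2, Table 1, add to the DLT set: excluding subjects regarded as not evaluable under Protocol 6.5.2, unless they had another DLT.
2. In IAP 15.1, cite Protocol 6.2.4 together with 6.5.2, so that an in-window transfusion or erythroid growth factor for a drug-related hemoglobin drop counts as a DLT.
3. Add the same exclusion line to Protocol Table 13 and the SMC iAP Dose Escalation set only if those documents are still open.

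The cost is one line and one cross-reference in the IAP. If such a case occurred, the evaluable denominator is slightly smaller. If none occurred, no result changes.

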### 6.5.3 Other Interventions

Interventions as indicated in the eligibility criteria in Section 5.3 are applicable.

### 6.5.4 Special Precautions

Special precautions on Day 1 and Day 15 of every cycle, vital signs (blood pressure, pulse, respiratory rate, temperature,) will be assessed predose (within 15 min of oral dosing and infusion), and then every 15 min **CCI** [REDACTED] during infusion and for an additional 2 h post-infusion. If vital signs are not stable after 2 h (either blood pressure  $> 140/ > 90$  mmHg or  $< 90/ < 60$  mmHg compared to normal blood pressure at start or changes of  $> 20$  reading points between measurements, for heart rate and respiration rate changes of  $\geq 20\%$  compared to start) then continue monitoring every 15 min until stable on 2 consecutive

repeated measurements. If vital signs are stable after 2 h, subjects will be monitored for vital signs every 60 min up to 8 h post-infusion on Days 1 and 15 of Cycle 1 only. These monitoring will be performed in an area with resuscitation equipment and emergency agents. In addition monitor subjects for signs/symptoms of infusion reactions including but not limited to pyrexia, chills, flushing, dyspnea, wheezing, back pain, abdominal pain, and urticaria. Interrupt or slow the rate of infusion for mild or moderate infusion-related reactions. **CCI**

Due to possible food effects on the PK of M4112, M4112 should be administered at least 1 h prior to a meal and at least 2 h after a meal.

Subjects will be instructed to avoid any intake of grapefruit, grapefruit juice, Seville oranges, Seville orange marmalade, or other products containing grapefruit or Seville oranges and cranberries within 7 days prior to Day 1 of M4112 administration and during M4112 administration. The same applies to herbal supplements which induce or inhibits CYP3A, including but not limited to St. John's wort. For further details, see the Drug Development and Drug Interactions website mentioned in Section [6.5.2](#).

The treatment recommendations for infusion-related reactions and severe hypersensitivity reactions according to the NCI are as outlined in Sections [6.5.5.1](#) and [6.5.5.2](#), respectively.

Investigators should also monitor subjects closely for potential irAEs, which may become manifest earliest after weeks of treatment. Such events may consist of persistent rash, diarrhea and colitis, autoimmune hepatitis, arthritis, glomerulonephritis, cardiomyopathy, or uveitis and other inflammatory eye conditions. The spectrum of hypothetical irAEs also includes formation of auto-antibodies like anti-nuclear antibodies (ANAs) or anti-neutrophil cytoplasmic antibodies (ANCAs). See Section [6.5.5.3](#) for details on the management of irAEs.

